4. OBJECTIVE(S)/SPECIFIC AIMS AND HYPOTHESES

- *A concise statement of the goal(s) of the current study.*
- *The rationale for and specific objectives of the study.*
- *The goals and the hypothesis to be tested should be stated.*

We believe the delivery of N-of-1 methodology through Personalized Trials is feasible to scale to a large randomized controlled trial, and eventually to standard clinical practice. In order to demonstrate this feasibility, we must be able to collect data illustrating that Personalized Trials can be a low-burden, satisfactory tool that can be scaled to individuals and clinicians.

We will additionally examine the novel individual-level heterogeneity of treatment effect and observed outcomes-made possible by the N-of-1 trial design, and will test the feasibility of pooling real-world N-of-1 results across patients to efficiently estimate the overall effectiveness of light therapy and thus the N-of-1 trial design. To determine whether this "precision therapeutics" paradigm-shifting approach

creates added value for the learning healthcare system, and to confirm engineering these innovations into one platform and system to empirically determine the precise therapy for each patient is feasible, we will pool N-of-1 results across all projects using the N1Thrive platform.

Thus, the goals of this pilot study are to:

1. Conduct a pilot test (N=60) of a Personalized Trial that is delivered remotely to participants in the United States.
2. Collect data regarding Minimum Viable Product (MVP) specifications for a future technology platform to deliver Personalized Trials.
3. Incorporate web-based research advertising and recruitment in the pilot study.
4. Elicit participant attitudes and opinions toward using Personalized Trials to help inform their personal wellness strategy.

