8. NUMBER OF SUBJECTS

- *Indicate the total number of subjects to be accrued locally. If applicable, distinguish between the number of subjects who are expected to be pre-screened, enrolled (consent obtained), randomized and complete the research procedures.*
- *If your study includes different cohorts, include the total number of subjects in each cohort.*
- *If this is multisite study, include total number of subjects across all sites.*

We expect to pre-screen up to 750 potential participants in this study. Up to 150 potential participants will be invited to enroll. Up to 60 participants will be randomized to complete research procedures.

Of those participants who receive randomized treatment schedules, 30 participants will be randomized to receive the protocol in the following order of two-week treatment periods: Bright Blue Light Therapy, Dim Blue Light Therapy, Usual Care, Usual Care, Dim Blue Light Therapy, Bright Blue Light Therapy (ABCCBA). The remaining 30 participants will be randomized in the following order of two-week treatment periods: Usual Care, Dim Blue Light Therapy, Bright Blue Light Therapy, Bright Blue Light Therapy, Dim Blue Light Therapy, Usual Care (CBAABC).

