10. ENDPOINTS

- *Describe the primary and secondary study endpoints*
- *Describe any primary or secondary safety endpoints*

This study is a feasibility pilot whose primary objective is to assess the acceptability, scalability of implementation and participant satisfaction with a personalized trial methodology to resolve a chronic complaint. Thus, the primary endpoint is trial completion in the first 3 months.

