Baseline participants that do not achieve at least 80% adherence of Fitbit wear and survey submission during the first 10 days of the baseline period will be withdrawn from the study. Those that maintain at least 80% adherence will be randomized to one of two treatment sequences in the pilot study. Participants who are randomized to receive treatment sequences will receive email confirmation including their protocol timeline. Participants will also receive a second mailed kit including a bright blue light commercial AYO light therapy device, and a dim blue light research AYO light therapy device. Enrollment will continue until up to 60 participants have been randomized into one of two treatment sequences.

Each treatment sequence is made up of 6 2-week periods dedicated to either bright blue light therapy, dim blue light therapy, or usual care. During both bright blue light and dim blue light therapy weeks, participants will receive a text message within an hour of their self-reported wake time instructing them to use their designated light therapy device for 30 minutes. During usual care treatment periods, participants will not receive any text notifications to complete light therapy, and will instead be asked to refrain from using either AYO device.

During all treatment weeks (12 weeks total), participants will be asked to continue wearing their Fitbit device each day and night. They will continue to receive 3 randomized text messages each day with questions about their fatigue, pain, concentration, confidence, mood, and stress at that current moment, as well as an

evening text asking them to reflect on their fatigue and any side-effects they may be experiencing from their light therapy treatment (if applicable). Participants will receive slightly longer surveys on Sunday evenings, asking them to reflect on their symptoms of fatigue that week. A study phone number and email address will be available as part of each survey to contact the study team if a participant is concerned about any side effects they are experiencing. Participants will also be instructed to stop their light therapy sessions if they are concerned about their side effects.

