12. STATISTICAL ANALYSIS

- *Describe how your data will be used to test the hypotheses.*
- *State clearly what variables will be tested and what statistical tests will be used.*
- *Include sample size calculations.*
- *If this is a pilot study, state which variables will be examined for hypothesis generation in later studies.*

The sample size of 60 participants was chosen to have a sufficient number of patients to obtain a preliminary assessment of the feasibility of personalized trials of light therapy for management of symptoms of fatigue. The numbers of questionnaires and treatment repetitions per trial were based on expert recommendations by a statistician and estimations about maximal duration of the trial to maintain patient engagement. Specifically, the primary endpoint is trial completion in the first 3 months. We aim to demonstrate a trial completion rate greater than 50% in randomized participants. With $n = 60$, using a one-sample binomial test at 2.5% significance one-sided, this will give us about 90% power if the true completion rate is 70%. Data will be reported transparently so that individual level heterogeneity can be assessed(21).

Participants will be randomized into one of two different treatment orders, ABCCBA or CBAABC, where A=bright light, B=dim light, and C=usual care. Two treatment orders were chosen to test out the feasibility of carrying out a virtual, N-of-1 study. ABCCBA was chosen as an order to test participant acceptability with back-to-back usual care treatment (i.e. no treatment) extending through 4 weeks. CBAABC was chosen as a companion treatment order to ABCCBA to test participant acceptability with starting a Personalized Trial with a usual care treatment after a baseline run-in (i.e. no treatment for the first 4 weeks). Treatment order was not included as a factor in the statistical analysis because acceptability and feasibility study.

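### The completion test covers only people who passed an 80% adherence run-in, so a result above 50% does not by itself support the unrestricted scalability claim

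*Combined protocol and SAP*

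**What the plan says.** **Entry to randomisation.** Under Section 11, people sign consent, are mailed a Fitbit and start a two-week baseline. A coordinator reviews their adherence at day 10. Those below 80% for Fitbit wear and surveys are withdrawn; for the rest, "Those that maintain at least 80% adherence will be randomized to one of two treatment sequences in the pilot study". Sections 12 and 16 repeat the 80% condition.

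**Endpoint and test.** Section 10 says "the primary endpoint is trial completion in the first 3 months". Section 12 names the population: "We aim to demonstrate a trial completion rate greater than 50% in randomized participants". This is the only hypothesis test on a feasibility outcome.

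**Other outcomes.** Section 12 lists usability, satisfaction, mean adherence to surveys, Fitbit and light devices, advertising and website metrics, and within-person symptom and activity summaries. None is a run-in pass rate or a completion rate among people who consented or started baseline.

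**The claim.** Section 4 holds that delivering the N-of-1 method "is feasible to scale to a large randomized controlled trial, and eventually to standard clinical practice". Section 2 says much the same, and Section 10 makes scalability of implementation part of the primary objective. None of the three limits the claim to people who pass an adherence screen.

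**The funnel.** Section 8 states: "Up to 150 potential participants will be invited to enroll". At most 60 are then randomised. The number expected to start baseline is not given.

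**The concern.** A person who consents, receives a kit, starts baseline and is withdrawn for low adherence has been lost to the method. Section 9 counts the two baseline weeks as part of the 14-week study. Section 11 describes finishing as going through baseline and six treatment periods, with withdrawal by the research team as one alternative. On that description a run-in failure is a non-completer, yet is absent from the tested rate.

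The screen also bears on the endpoint. The screened tasks, Fitbit wear and surveys, continue through all 12 treatment weeks, and Section 16 makes poor adherence a ground for involuntary withdrawal. The run-in therefore tends to remove people who would be more likely not to complete.

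At stake is how a success would be read. More than 50% of randomised participants could complete while half or fewer of those who started did so, and no planned outcome would show it.

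**Working it through.** **1. The plan's own figure.** Inputs from Section 12: n = 60, null rate 0.50, true rate 0.70, and the test specified as "using a one-sample binomial test at 2.5% significance one-sided", with a stated power of about 90%.

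- Normal approximation: standard error under the null √(0.25/60) = 0.0645; under the alternative √(0.21/60) = 0.0592. Power = Φ((0.20 − 1.96 × 0.0645)/0.0592) = Φ(1.24) = 0.893. The stated figure reproduces.
- Exact binomial: the smallest count with a null tail of at most 0.025 is 39 (tail 0.0137; for 38 it is 0.0259). Power at 0.70 is 0.838.

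So 39/60 = 65% is the smallest exactly significant result.

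**2. Completion per baseline starter.** Let q be the run-in pass rate and c the completion rate among randomised participants. With run-in failures counted as non-completers, and everyone who passes randomised, completion per starter = q × c. The documents do not give q, so it is assumed over a range, with 60 randomised.

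| Assumed q | Starters (60/q) | c = 42/60 | c = 39/60 |
|---|---|---|---|
| 95% | 63 | 66.5% | 61.75% |
| 90% | 67 | 63% | 58.5% |
| 80% | 75 | 56% | 52% |
| 70% | 86 | 49% | 45.5% |
| 60% | 100 | 42% | 39% |

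**3. Where the per-starter rate falls to 50%.**

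- At 42/60: q = 0.50/0.70 = 71.4%, or 84 starters (42/84 = 50%).
- At 39/60: q = 0.50/0.65 = 76.9%, or 78 starters (39/78 = 50%).

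**4. Precision.** Exact (Clopper-Pearson) 95% intervals in whole people:

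- 42/67: 50.0% to 74.2%
- 42/75: 44.1% to 67.5%
- 42/100: 32.2% to 52.3%

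**5. Should the test move to all starters?** Suppose 60 are randomised, true completion among them is 70%, and the same exact test is applied to all starters. With 67 starters, 42 completers are needed and power is 56%. With 75 starters, 47 are needed and power is 10%. Without run-in loss it is 84%. The study is not sized for that test, so the per-starter rate should be estimated, not tested.

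**The case against.** The plan has a fair defence. It states its denominator openly, consent warns people that they may be removed before randomisation (Section 16), and the run-in is part of the method being piloted. A rate conditional on the run-in is what a later trial with the same run-in would need. The scaling statements in Sections 2 and 4 are worded as beliefs, and Section 2 lists other supporting data, such as adherence, engagement and satisfaction. Section 12 is modest about its aim: "The sample size of 60 participants was chosen to have a sufficient number of patients to obtain a preliminary assessment of the feasibility". Low Fitbit adherence at day 10 may also reflect syncing or device problems; the documents give no reasons for run-in failure.

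Most of this stands. The test is valid for its stated population, completion is not the only evidence, and at a pass rate of 90% or more the per-starter figure stays at 58.5% or higher even for the smallest significant result. It does not close the gap, because Section 10 ties scalability to the completion endpoint and none of the other listed outcomes measures loss at the run-in.

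Three stronger readings are tempting and are not supported:

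- *The run-in and the endpoint measure the same behaviour.* Completion carries no adherence threshold, covers 12 further weeks and adds light therapy, which baseline does not test. The two are closely related only.
- *The result cannot support feasibility at all.* It does, for people who pass the run-in.
- *Completion is really 42/150 = 28%.* The 150 is a ceiling on people invited, who must still have a phone call, answer the comprehension questions and sign consent before baseline. It is not a count of starters.

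**Conclusion.** The point holds as a mismatch between a conditional test and an unconditional claim. It is not an error in the test. A completion rate above 50% among randomised participants does not by itself show that the method can be scaled among people who consent and start, and still less in standard clinical practice.

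The size rests on an unknown pass rate. The gap is modest at 90% to 95%. At about 77% or lower, a just-significant success means that half or fewer of the starters completed; at the planning rate of 70% completion, this happens at about 71% or lower. These figures assume 60 randomised, everyone who passes randomised, and run-in failures counted as non-completers. The plan should be changed because no listed outcome would show which case applies.

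**What to change.** 1. Keep the powered test in Section 12 unchanged, and label its result as completion among run-in-adherent participants.
2. Add as a named feasibility outcome in Section 12: (a) the run-in pass rate, and (b) completers divided by all who consented and started baseline, with run-in failures counted as non-completers. Give an exact 95% confidence interval for each, and no new test.
3. Base the scalability conclusion (Sections 2, 4 and 10) on rate (b), or limit it in words to people who pass the run-in.
4. Define completion, since both rates need it. Reconcile the run-in window, which Section 11 gives as the first 10 days and Section 12 as the whole run-in, so that a run-in failure is unambiguous.

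The cost is two extra proportions. The data should already be held, because each starter's adherence is reviewed at day 10. Sample size and power do not change. The price is a headline figure that will be less favourable if anyone fails the run-in.

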Once potential participants successfully submits their signed consent form, they will receive an onboarding questionnaire to collect more information including a cell phone number and home address. A consenting coordinator will review this information and send the potential participant an email which will include a confirmation of the start date of their baseline period, as well as a short video of what to expect during onboarding to the study. They will be mailed an initial study kit including a Fitbit Charge 3 device and a printed copy of their electronically-

signed HIPAA authorization and consent form with a URL to view the informed consent video that they watched previously. Potential participants will be asked to download the Fitbit app to their smart phone. All baseline periods will begin on a Monday. No more than 20 participants will be permitted to begin on the same day.

The baseline period will take place over the course of 2 weeks. Potential participants will not use light therapy during the baseline period. At three randomized times each day during waking hours, (identified by the potential participant during their onboarding survey), baseline participants will receive a text message asking them to rate their fatigue, pain, concentration, confidence, mood, and stress levels at that exact moment. Each evening, baseline participants will receive a survey asking a few questions about their fatigue that day. At the end of the week on Sunday evenings, baseline participants will receive a slightly longer survey asking them to reflect on their symptoms of fatigue that week.

During the baseline period, potential participants will be asked to wear their Fitbit all day and night, even while they are sleeping. Baseline participants will be instructed to sync their Fitbit device by opening the Fitbit app on their phone at least every two days.

Ten days into the baseline period, a consenting coordinator will review individual adherence to Fitbit wear and to survey responses. Adherence to Fitbit wear will be defined as recorded activity of greater than 12 hours a day, and recorded sleeping activity. Survey adherence will be defined as submission of a given survey.

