Participants may receive additional text messages to those outlined above with important reminders about their protocol (e.g. transition to a new treatment period), or to remind participants to sync their data. We will send a maximum of 6 text messages per day during the study, including these reminders and the survey questions outlined above.

In the event of an unanticipated circumstance that temporarily prevents a participant from completing study activities (illness, injury, death in the family, etc.), the participant will have the option of pausing their study to resume once their circumstance has been positively resolved.

Participants will complete remote data monitoring after they have gone through one baseline period (two weeks), two bright blue light therapy periods (two weeks each), two dim blue light therapy periods (two weeks each), and two usual care periods (two weeks each), or 14 weeks total. Alternatively, a participant may choose to withdraw from the study, or be withdrawn from the study by the research team. Upon completion of data monitoring, participants will be given instructions on how to un-link their Fitbit from the study account. Daily text messages and survey prompts will be cancelled for participants who are withdrawn from the study.

We will compile the self-reported data from questionnaires, treatment adherence, side effects, pain, fatigue, concentration, confidence, mood, and stress assessments, as well as information from the Fitbit regarding activity (steps, flights climbed and intensity), sleep (duration, estimated sleep stages) for each individual participant. Treatment adherence will be tracked via an AYO research web portal and will be included in the compiled data. No identifying information will be provided to AYO or included on the treatment adherence report provided by AYO. We will analyze this data and create a summary report of the participant's data and symptoms over the study period, relation to the bright blue light therapy, dim blue light therapy, and usual care treatment periods.

The participant will be sent this report in an encrypted email and secure web link by our study team. Participants will also be sent links to several online videos explaining the terms and data visualizations available in their summary report. These videos will be general to the template report and will not contain any

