- Google Ad metrics
- Social media activity, including but not limited to:
 - Social media conversion rate, defined as total impressions compared to total click-through
 - Cost per social media conversion
- Website activity, including but not limited to:

- Total number of website visits per traffic source
- Website bounce rates
- Mean user total time on website

In order to share a summary report of observed trends back to the participant to assess acceptability and satisfaction with the participant report, additional outcomes will be analyzed on an N-of-1 level including:

- Mean Within-Subject Difference in Self-Reported Daily Fatigue During 3 Treatment Periods from Mean Baseline using the PROMIS Item Bank v1.0 – Fatigue 7b Daily Short Form
- Mean Within-Subject Difference in Self-Reported Weekly Fatigue During 3 Treatment Periods from Mean Baseline, using the PROMIS Item Bank v1.0 – Fatigue 8a Short Form
- Mean Within-Subject Difference in Ecological Momentary Assessment Three-Times-Daily of Pain During 3 Treatment Periods from Mean Baseline, using the Numeric Pain Rating Scale adapted from McCaffery, Beebe et al. 1989
- Mean Within-Subject Difference in Ecological Momentary Assessment Three-Times-Daily of Fatigue During 3 Treatment Periods from Mean Baseline, using the Numeric Pain Rating Scale adapted from McCaffery, Beebe et al. 1989
- Mean Within-Subject Difference in Ecological Momentary Assessment Three-Times-Daily of Concentration During 3 Treatment Periods from Mean Baseline, using the Numeric Pain Rating Scale adapted from McCaffery, Beebe et al. 1989
- Mean Within-Subject Difference in Ecological Momentary Assessment Three-Times-Daily of Confidence During 3 Treatment Periods from Mean Baseline, using the Numeric Pain Rating Scale adapted from McCaffery, Beebe et al. 1989
- Mean Within-Subject Difference in Ecological Momentary Assessment Three-Times-Daily of Mood During 3 Treatment Periods from Mean Baseline, using the Numeric Pain Rating Scale adapted from McCaffery, Beebe et al. 1989
- Mean Within-Subject Difference in Ecological Momentary Assessment Three-Times-Daily of Stress During 3 Treatment Periods from Mean Baseline, using the Numeric Pain Rating Scale adapted from McCaffery, Beebe et al. 1989
- Mean Within-Subject Difference in Self-Reported Side Effects from Baseline, using the average number of days side effects were reported during treatment periods.

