17. RISKS TO SUBJECTS

- *Describe any potential risks and discomforts to the subject (physical, psychological, social, legal, or other) and assess their likelihood and seriousness and whether side effects are reversible. Where appropriate, describe alternative treatments and procedures that might be advantageous to the subjects.*
- *Include risks to others , like sexual partners (if appropriate)*
- *Discuss why the risks to subjects are reasonable in relation to the anticipated benefits and in relation to the importance of the knowledge that may reasonably be expected to results*
- *Describe the procedures for protecting against or minimizing any potential risks, including risks to confidentiality, and assess their likely effectiveness.*

This study poses low risk of physical harm to subjects. Bright blue light therapy is a mainstream treatment for fatigue symptoms. Several transient side-effects have been observed when monitoring patients including jumpiness/jitteriness, headache, and nausea, and mania has been infrequently observed in patients with bipolar disorder. These side-effects typically resolve soon after cessation of light therapy. Monitoring for adverse side-effects will be performed during the N-of-1 trial. Subjects will be encouraged to adhere to the light therapy protocol, but will also be told that they can discontinue treatment at any time.

AYO glasses have 4 Light-emitting diodes (LEDs) with a dominant wavelength of approximately $470\text{nm} \pm 2\text{nm}$ and typical irradiance (100% intensity) of approximately $250\text{ }\mu\text{W/cm}^2$. Although there are minimal direct safety standards for blue light within the United States, the photochemical blue light hazard can be evaluated based on several global standards. AYO glasses are compliant with the following: Directive 2014/30/EU (EMC) EN 55014-1:2006 + A2:2011 EN 55014-2:2015, Directive 2011/65/EU (RoHS), IEC 62321:2008, IEC 62321-3-1:2013, IEC 62321-4:2013, IEC 62321-5:2013, Radio-Equipment Directive 2014/53/EU, EN 62479:2010, EN 300328:2015, EN 301489-1:2011, EN 301489-17:2012, RoHS Directive 2011/65/EU of the European Parliament, the Council from 08/06/2011 on restriction of the use of certain hazardous substances in electrical and electronic appliances, and with the international standard and conformity assessment IEC 62471 “Photobiological safety of lamps and lamp systems.”

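### Side effects are to be contrasted with baseline and reported by condition, but no like-for-like side-effect question is described for baseline or usual care

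*Combined protocol and SAP*

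**What the plan says.** Five statements in the combined protocol and SAP bear on this point.

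- **Baseline evening survey (Section 11).** "Each evening, baseline participants will receive a survey asking a few questions about their fatigue that day". No side-effect or symptom item is described for these two weeks.
- **Evening text in treatment weeks (Section 11).** The description covers all 12 treatment weeks. Besides fatigue, the evening text asks about "any side-effects they may be experiencing from their light therapy treatment (if applicable".
- **Usual care (Section 11).** In these blocks "participants will not receive any text notifications to complete light therapy, and will instead be asked to refrain from using either AYO device".
- **Participant report (Section 11).** Side effects are among the data compiled for each participant. The report then presents data and symptoms in "relation to the bright blue light therapy, dim blue light therapy, and usual care treatment periods".
- **Outcome definition (Section 12).** "Mean Within-Subject Difference in Self-Reported Side Effects from Baseline, using the average number of days side effects were reported during treatment periods".

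Section 17 names the effects expected: "Several transient side-effects have been observed when monitoring patients including jumpiness/jitteriness, headache, and nausea". Section 3 gives one purpose of usual care as controlling for expectancy in self-reported data.

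**The concern.** A difference from baseline needs the same quantity measured at baseline, and a report by condition needs the same question asked in each condition. As described, neither holds for side effects. The one systematic item asks for effects caused by light, so it yields a meaningful count only while a light is in use.

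The expected effects are non-specific: people have headaches and nausea without light therapy. On light days the participant knows a device is in use and decides whether a symptom came from it. On baseline and usual-care evenings the same symptom has no equivalent place to be recorded. A contrast of light with no light therefore carries whatever part of the background symptom rate is attributed to the device.

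What is at stake is the individual report. Section 2 says participants should be able to choose a preferred intervention, if any, from their data. A side-effect entry that leans against both lights could distort that choice.

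**Working it through.** The plan states no side-effect rate, so there is no figure to reproduce. The check has two parts: the text, then an illustration on assumed rates.

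**1. What the item can yield in each condition**

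| Condition | Days | Described evening side-effect item | Usable count |
|---|---|---|---|
| Baseline | 14 | None; fatigue only | None described |
| Bright | 2 × 14 = 28 | Effects from light therapy | Symptoms attributed to light |
| Dim | 2 × 14 = 28 | Effects from light therapy | Symptoms attributed to light |
| Usual care | 2 × 14 = 28 | Same wording, where applicable | Not comparable |

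For usual care the text allows two readings. If the item is dropped, the count is missing. If it is shown, it asks about a treatment the participant has been told not to use, and the natural answer is none. Neither is the same measurement as on a light day.

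Share of days without a like-for-like count:
- randomised days: 28 / 84 = 33%
- with baseline: (28 + 14) / (84 + 14) = 42 / 98 = 43%

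The outcome definition adds a further ambiguity. It averages days over treatment periods without splitting by condition, and Section 11 also calls usual-care blocks treatment periods. It is therefore unclear which blocks enter the average.

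**2. Size of the possible false excess (assumed inputs)**

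Let *p* be the daily rate of headache, nausea or jitteriness unrelated to light, and *f* the share of such days the participant attributes to the device. Neither is in the documents. I take *p* = 5%, 10%, 20% and *f* = 20%, 50%, 100%. For an inert light:

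expected false side-effect days per 28-day condition = 28 × *p* × *f*

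| | *f* = 20% | *f* = 50% | *f* = 100% |
|---|---|---|---|
| *p* = 5% | 0.28 | 0.70 | 1.4 |
| *p* = 10% | 0.56 | 1.4 | 2.8 |
| *p* = 20% | 1.12 | 2.8 | 5.6 |

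Against a baseline or usual-care count taken as zero, this is an apparent excess of 1 to 20 percentage points of days (*p* × *f* = 0.01 to 0.20).

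The chance that one participant has at least one such day on a given light, treating days as independent, is 1 − (1 − *pf*)^28. It is 24.5% at *pf* = 0.01, 76.2% at 0.05 and 99.8% at 0.20. This is not the planned outcome; it only shows how easily a single report could be touched.

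**3. Bright versus dim**

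Both lights get the same item. With equal *p* and *f*, the expected difference is 28*pf* − 28*pf* = 0. The asymmetry affects light versus baseline and light versus usual care, not bright versus dim.

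**The case against.** The other side has several good arguments, and most of them limit the point.

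- **Usual care is not without harm data.** Every survey carries contact details for anyone concerned about side effects, and pain, mood, stress, concentration, confidence and fatigue are rated three times daily, without attribution, in baseline and all blocks. A reader might infer that harms go wholly unrecorded in usual care; the documents do not support that. However, the contact route is passive, and headache, nausea and jitteriness have no item of their own in those ratings.
- **The survey wording itself is not in the documents.** Section 11 paraphrases it and does not say whether the item is hidden, shown or reworded in usual care. It is tempting to conclude that reports will show side effects on both lights and zero on usual care. That is a prediction, not something the plan states.
- **Ordinary symptoms are not automatically counted as harms of the light.** They count only if the participant attributes them to it. This is a risk whose size depends on *f*.
- **Dim light is a same-question comparator.** This stands, subject to equal attribution. It does not supply the missing comparison with no light, and Section 3 names usual care as the control condition.
- **A knock-on effect on withdrawal or completion does not follow.** In Section 16, removal of a device runs through participants contacting the team, and withdrawal for adverse effects is not tied to the evening item.
- **The off-target examples in Section 3 are unaffected.** Stress and physical activity are measured by ratings and Fitbit throughout.
- **The stakes are modest.** This is a feasibility pilot, the endpoint in Section 10 is trial completion, and Section 23 leaves safety and efficacy to later trials.

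What remains is that the described baseline survey cannot supply the baseline value Section 12 needs, and usual care has no comparable count.

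**Conclusion.** The point holds in this form: no systematic, like-for-like side-effect item is described for baseline or usual care, so side-effect contrasts of light with either one have no valid comparator and can lean against light. The clearest evidence is the fatigue-only baseline survey in Section 11 set against the difference from baseline in Section 12.

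The firm figures are 28 of 84 randomised days, or 42 of 98 with baseline. The false excess of 0.28 to 5.6 days per 28 rests entirely on the assumed *p* and *f* and on an inert light. Independence between days matters only for the chance of at least one such day.

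The matter is worth correcting before data collection, because a symptom not asked about on the day cannot be reliably recovered later. It does not touch the primary endpoint or the power statement.

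**What to change.** **Section 11, baseline and treatment weeks.** Ask one identical item every evening of baseline and of all six blocks: whether the participant had headache, nausea, jitteriness or another symptom that day, with no mention of light. Record perceived relation to light as a separate item, kept for safety contact and not used as the outcome.

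**Section 12.** Define the outcome as the proportion of answered evenings with any symptom, by condition. State the contrasts: bright minus usual care, dim minus usual care, and bright minus dim. Any difference from baseline should use the same item. A proportion is needed because baseline has 14 days and each condition 28, and because evenings will be missed.

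If the actual survey is already neutral and asked every evening, only the descriptions in Sections 11 and 12 need correcting.

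**Cost.** A wording change to a survey already sent daily, and a minor amendment; no extra contacts. Participants answer one more short item on baseline and usual-care evenings, and usual care will show non-zero symptom reports. The neutral item equalises what is asked. It does not remove expectancy, since participants still know when a device is in use.
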